1.2.1.1 Non-clinical experience

Everolimus inhibits the proliferation of a range of human tumor cell lines *in vitro* including lines originating from lung, breast, prostate, colon, melanoma and glioblastoma. IC50s range from sub/low nM to μ M. Everolimus also inhibits the proliferation of human umbilical vein endothelial cells (HUVECS) *in vitro*, with particular potency against VEGF-induced proliferation suggesting that everolimus may also act as an anti-angiogenic agent. The anti-angiogenic activity of everolimus was confirmed *in vivo*. Everolimus selectively inhibited VEGF-dependent angiogenic response at well tolerated doses. Mice with primary and metastatic tumors treated with everolimus showed a significant reduction in blood vessel density when compared to controls.

The potential of everolimus as an anti-cancer agent was shown in rodent models. Everolimus is orally bioavailable, residing longer in tumor tissue than in plasma in a subcutaneous mouse xenograft model, and demonstrating high tumor penetration in a rat pancreatic tumor model. The pharmacokinetic profile of everolimus indicates sufficient tumor penetration, above that needed to inhibit the proliferation of endothelial cells and tumor cell lines deemed sensitive to everolimus *in vitro*.

Everolimus administered orally daily was a potent inhibitor of tumor growth, at well tolerated doses, in 11 different mouse xenograft models (including pancreatic, colon, epidermoid, lung and melanoma) and two syngeneic models (rat pancreatic, mouse orthotopic melanoma). These models included tumor lines considered sensitive and “relatively resistant” *in vitro*. In general, everolimus was better tolerated in mouse xenograft models than standard cytotoxic agents (i.e., doxorubicin and 5-fluorouracil), while possessing similar anti-tumor activity. Additionally, activity in a VEGF-impregnated subcutaneous implant model of angiogenesis and reduced vascularity (vessel density) of everolimus-treated tumors (murine melanoma) provided evidence of *in vivo* effects of angiogenesis.

It is not clear which molecular determinants predict responsiveness of tumor cells to everolimus. Molecular analysis has revealed that relative sensitivity to everolimus *in vitro* correlates with the degree of phosphorylation (activation) of the AKT/PKB protein kinase and the S6 ribosomal protein; in some cases (i.e., glioblastoma) there is also a correlation with PTEN status.

In vivo studies investigating the anti-tumor activity of everolimus in experimental animal tumor models showed that everolimus monotherapy typically reduced tumor cell growth rates rather than produced regressions. These effects occurred within the dose range of 2.5 mg to 10 mg/kg, orally once a day.

In preclinical models, the administration of everolimus is associated with reduction of protein phosphorylation in target proteins downstream of mTOR, notably phosphorylated S6 (p-S6) and p-4E-BP1, and occasionally with an increase in phosphorylated AKT, a protein upstream of mTOR signaling pathway.

All significant adverse events observed in toxicology studies with everolimus in mice, rats, monkeys and mini-pigs were consistent with its anticipated pharmacological action as an anti-proliferative and immunosuppressant and at least in part reversible after a 2 or 4-week recovery period with the exception of the changes in male reproductive organs, most notably testes.

Further details can be found in the [everolimus IB] and/or the locally approved prescribing information.

1.2.1.2 Clinical experience

Several lines of evidence suggest that the mTOR pathway is involved in the pathogenesis of NETs. For example, patients with defects in the TSC2 gene, whose protein product inhibits mTOR activation, develop pancreatic neuroendocrine tumours (pNETs). Loss of the NF1 gene, which also regulates mTOR activity, is associated with the development of GI NETs in patients with neurofibromatosis. Sporadic NETs have been shown to coexpress insulin-like growth factor (IGF-1) and the IGF1 receptor (IGF-1R). Activation of the IGF-1/IGF-1R pathway activates mTOR leading to increased cell proliferation (Yao 2008b). Lastly, gene expression profiling studies show inhibition of the TSC2 and PTEN genes, both of which act as negative regulators of the PI3K/Akt/mTOR pathway, in most tumor samples from patients with pNETs, with lower levels of expression being associated with shorter disease-free and overall survival (Missiaglia 2010).

Based on these observations, a phase II clinical trial conducted by J. Yao at the MD Anderson Cancer Center studied everolimus and octreotide LAR in advanced low grade neuroendocrine carcinoma (Yao 2008b). A total of 60 evaluable patients were treated in two cohorts; patients received either everolimus at 5mg/day or 10 mg/day. Out of the sixty treated patients, 30 had carcinoid, and 30 islet cell tumours. Sixty-five percent of the patients were in progression at the time of study entry. Overall, 12 (20%) patients were reported to have partial response (4 carcinoids and 8 islet cell tumours, respectively), 43 (72%) had stable disease (25 in carcinoids and 18 in islet cell, respectively) and 5 (8%) had progressive disease (1 in carcinoids and 4 in islet cell, respectively) per RECIST. Overall median progression free survival (PFS) was 59 weeks (64 weeks in carcinoids and 50 in islet cell tumours, respectively). Median overall survival (OS) was not reached, with a 2 yrs survival rate of 78%. The combination of everolimus and octreotide LAR 30 mg appears to have been well tolerated. The most common toxicity reported was mucositis. CTC Grade 3/4 toxicities reported included: anemia, thrombocytopenia, aphthous ulcer, diarrhea, edema, fatigue, hypoglycemia, nausea, pain, and rash.

Subsequently, a second phase II open label, parallel group study was conducted in patients with advanced pancreatic neuroendocrine tumors (pNETs). Patients received either everolimus 10 mg daily as monotherapy (stratum 1; n = 115) or everolimus 10 mg daily in combination with \leq 30 mg octreotide LAR q 28 days (stratum 2; n = 45), based on prior octreotide LAR treatment (Yao 2010a). In stratum 1, there were 11 partial responses (9.6%), 78 patients with stable disease (67.8%), and 16 patients with progressive disease (13.9%); median progression-free survival was 9.7 months. In stratum 2, there were two partial responses (4.4%), 36 patients with stable disease (80%), and no patient with progressive disease. Median progression-free survival (PFS) was 16.7 months.

Two Phase III studies have recently provided additional evidence that everolimus has promising activity in patients with advanced neuroendocrine tumors.

[CRAD001C2324] is a phase III randomized double blind study of everolimus + best supportive care (BSC) vs. placebo + BSC in patients with pancreatic neuroendocrine tumors who have radiological documentation of disease progression within 12 months prior to randomization (Yao 2011). Patients were randomized 1:1 to receive either everolimus 10 mg once daily (n = 207) or placebo (n = 203). Patients in the placebo arm were allowed to crossover upon disease progression. Patients were stratified by prior cytotoxic chemotherapy and WHO performance status. The primary endpoint was progression free survival. Median progression free survival was 11.04 months for everolimus compared to 4.60 months for placebo (HR=0.35; 95% confidence interval, 0.27 to 0.45; p <0.0001). No statistically significant difference in overall survival between the two arms was seen. The most common adverse reactions (occurring > 20%) in the everolimus arm included: stomatitis (53.9%), rash (52.5%), diarrhea (46.6%), fatigue (43.6%), peripheral edema (35.8%), nausea (31.9%), headache (29.9%), pyrexia (29.4%), decreased appetite (28.9%), vomiting (28.4%), weight loss (27.9%), abdominal pain (23.5%), anemia (22.1%), cough (21.6%) and epistaxis (21.1%).

Study [CRAD001C2325] is a Phase III randomized double blind study of everolimus in combination with octreotide LAR versus placebo + octreotide LAR in patients with advanced low or intermediate grade NET with a history of secretory symptoms and radiological documentation of disease progression within 12 months prior to randomization (Pavel 2011). Patients were randomized 1:1 to receive either everolimus 10 mg once daily + octreotide LAR 30 mg once every 28 days (n = 216) or placebo + octreotide LAR 30 mg once every 28 days (n = 213). Patients in the placebo + octreotide LAR arm were allowed to crossover to treatment with open label everolimus + octreotide LAR upon disease progression. The primary endpoint was progression free survival (PFS) by central radiology review (adjudicated central review). Median progression free survival was 16.4 months for everolimus + octreotide LAR compared to 11.3 months for placebo + octreotide LAR (HR=0.77; 95% confidence interval, 0.59 to 1.00; p=0.026 vs. P=0.0246 pre-specified). Median PFS by investigator assessment was 12.0 months for everolimus + octreotide LAR compared to 8.6 months for placebo + octreotide LAR (HR=0.78; 95% confidence interval, 0.62 to 0.98; p=0.018). Adjusting for different censoring patterns, loss of power, and baseline imbalances between the two treatment arms, the Inverse Probability of Censoring Weights (IPCW) adjusted PFS, which was pre-specified in the study, demonstrated a consistent benefit in favor of everolimus + octreotide LAR (HR=0.60; 95% confidence interval, 0.44 to 0.84; p=0.0014). No statistically significant difference in overall survival between the two arms was seen. The most common adverse reactions (occurring \geq 20%) in the everolimus + octreotide LAR arm included: stomatitis (62%), rash (37%), fatigue (31%), diarrhea (27%), nausea (20%) and infections (20%).

Study [CRAD001T2302] included patients with advanced, progressive non-functional NET of GI or lung origin. Everolimus demonstrated superiority over placebo in terms of PFS showing a 52% relative risk reduction of progression/death in favor of everolimus (HR: 0.48; 95% CI: 0.35, 0.67) (p<0.001) (Yao 2016)). Based on these results, submissions worldwide have led to marketing authorization of everolimus in progressive, nonfunctional NET of GI or lung origin in over 41 countries including the US, EU, Canada, and Japan.

2 Rationale

2.1 Study rationale and purpose

In China, everolimus (Afinitor[®]) has been approved for the treatment of patients with local advanced, unresectable or metastatic, well differentiated progressive pancreatic neuroendocrine tumors (pNET) without safety and efficacy data in Chinese patients.

Thus this study is a post-approval commitment to China CFDA's request to collect the safety and efficacy data of everolimus in Chinese adult patients within this indication.

2.2 Rationale for the study design

This is a single arm, open-label study. The inclusion and exclusion criteria, as well as the dosing and dose modification criteria are designed according to the approved Chinese Package Insert (PI).

The primary variable corresponding to the main objective of the study is the safety profile in terms of adverse events, serious adverse events, adverse events suspected to be related to study drug and Grade 3 and 4 AEs. In addition, the incidences of specific adverse events of non-infectious pneumonitis as requested by CDE will be determined. For a complete list of the adverse events of special interest refer to [Section 8.1.3](#).

Efficacy endpoint will be the same as the primary endpoint in global phase 3 study CRAD001C2324, i.e. progression free survival (PFS), and the 5 year OS data as required by CDE in the approval letter.

This is an interventional study. In order to minimize the risk of low data quality, interval of visit schedule is relatively fixed. The population and dosing chosen for this study are all within label indication and the test are all suggested by approved Chinese PI for safety consideration.

2.3 Rationale for dose and regimen selection

Starting dose and dose adjustment will follow the approved Chinese Package Insert. The starting dose is 10 mg once daily. The subsequent dose levels are subject to change due to severe or intolerable adverse reactions, change of liver function, changes in concomitant drug use (refer to [Section 6.3.1](#)).

2.4 Rationale for choice of combination drugs

Not applicable

2.5 Rationale for choice of comparators drugs

Not applicable

2.6 Risks and benefits

Appropriate eligibility criteria as well as specific dose modification and stopping rules, are included in this protocol. Recommended guidelines for prophylactic or supportive management of study-drug induced adverse events are provided in [Section 6.3.1](#). The risk to subjects in this trial may be minimized by compliance with the eligibility criteria and study procedures, as well as, close clinical monitoring and targeted follow up checklist use for specific adverse events. There may be unforeseen risks with study treatment which could be serious including: Onset of benign or malignant tumors; potential risks related to missing information for the specific study population, e.g. Patients with uncontrolled cardiac disease etc.

3 Objectives and endpoints

To evaluate safety and efficacy of everolimus (Afinitor[®]) in Chinese adult patients with local advanced, unresectable or metastatic, well differentiated progressive pancreatic neuroendocrine tumors.

Objectives and related endpoints are described in [Table 3-1](#).

Table 3-1 Objectives and related endpoints

[figure not shown]
Objective	Endpoint	Analysis
Primary		Refer to Section 10.4
To evaluate the safety of treatment with Afinitor in Chinese adult patients with well differentiated progressive p-NET	
Incidences of AEs, AE suspected to be related to Afinitor, Grade 3/4 AEs and SAEs
 
Listing of AEs with special interest:
 
Non-infectious pneumonitis
	
Secondary		Refer to Section 10.5
To evaluate the overall efficacy of treatment with Afinitor in Chinese patients with well differentiated progressive p-NET	
• Overall Survival : defined as time from study treatment to death due to any cause.• Progression free survival : defined as time from first dose of study treatment to progression or death due to any cause	
Other secondary	Not applicable	Not applicable

4 Study design

4.1 Description of study design

Patient who are eligible will be provided with everolimus by sponsor to treat pNET and will follow the visit schedule in [Table 7-1](#) to collect safety and efficacy data until disease progression, unacceptable toxicity, death, protocol deviation or other reason that may lead to discontinuation before the end of study. All patients will be followed-up for survival status every 6 months by the investigator until death, lost to follow-up, withdrawal of consent for survival or end of study. If the patient is still on treatment after 2 years, he/she will be shifted to commercial drug. However, this shift has no impact on participation in the study, all assessments will continue as before.

Figure 4-1 Study design

4.2 Timing of interim analyses and design adaptations

Interim analysis is planned for this study to provide a snapshot of data available to CFDA for license renewal. Based on the license renewal timeline, an interim analysis is planned in July 2017 with approximate 30 patients enrolled.

4.3 Definition of end of the study

The “End of study” is defined as either at least 75% of patients have completed survival follow up or all patients discontinued study treatment or the last patient finished 5-year survival follow up, whichever comes first. Final analysis will be conducted at the end of the study. Additional analyses between interim analyses (IA) and final analysis might be performed per Center for Drug Evaluation (CDE)’s request.

4.4 Early study termination

The study can be terminated at any time for any reason by Novartis. Should this be necessary, the patient should be seen as soon as possible and the same assessments should be performed as described in [Section 7](#) for a prematurely withdrawn patient. The investigator may be informed of additional procedures to be followed in order to ensure that adequate consideration is given to the protection of the patient’s interests. The investigator will be responsible for informing IRBs and/or ECs of the early termination of the trial.

5 Population

5.1 Patient population

The patient population includes Chinese adult patients with unresectable, locally advanced or metastatic, G1 or G2 progressive pancreatic neuroendocrine tumors (pNET) (WHO 2010). The planned sample size will be approximately 60patients with 30 additional patients enrolled after protocol amendment (v01).

The investigator or designee must ensure that only patients who meet all the following inclusion and none of the exclusion criteria are offered treatment in the study.

5.2 Inclusion criteria

Patients eligible for inclusion in this study have to meet **all** of the following criteria:

Written informed consent must be obtained prior to any screening procedures

1. Chinese Adult patients \geq 18 years of age
2. Patients must have histological confirmed G1 or G2 locally advanced, unresectable pancreatic neuroendocrine tumors(pNETs) (WHO 2010)
3. Patients must have radiological documentation of progression of disease per RECIST 1.1 within 12 months prior to enrollment.
4. Measurable disease per RECIST 1.1 criteria using triphasic computed tomography (CT) scan or multiphase MRI for radiologic assessment.
5. Afinitor treatment which is recommended by the treating physician.

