Safety assessments	Incidences of AEs, AE suspected to be related to Afinitor, Grade 3/4 AEs and SAEs
Other assessments	Not applicable to this study
Data analysis	Descriptive Statistics for safety variables and efficacy assessment, will be provided through tables and listings whereas applicable.
Key words	Everolimus (Afinitor®), locally advanced, unresectable or metastatic, well differentiated progressive pancreatic neuroendocrine tumors, safety, efficacy

Amendment 1 (31-May-2017)

Amendment rationale

The main purpose of the amendment is:

- To increase the sample size from approximately 30 to 60 patients to collect additional safety and efficacy data of everolimus in Chinese adult patients with pNET to meet the post-approval commitment request from CFDA.
- To update format according to new template.
- To fix wording, spelling and punctuation.

First patient first visit (FPFV) of this study was on 14-Mar-2016 and 31 patients had been enrolled by Nov 2016.

Changes to the protocol

Changes to specific sections of the protocol are shown in the track changes version of the protocol using strike through red font for deletions and red underlined for insertions.

The following changes have been implemented:

- Section 1.1, 2.1, 3, 5.1, 5.2, 10.8: To add “unresectable” to clearly identify population. Section 1.2.1 and 1.2.1.1: Update approved indication and registry study’s brief result.
- Section 1.2.1.1: Add non-clinical experience.
- Section 2.4, 2.5, 6.1.2, 6.1.3, 6.4.4, 7.1.1, 7.1.2.1, 7.1.3, 7.1.5.1, 7.1.7, 7.1.8, 7.2.2.6, 7.2.2.7, 7.2.2.8, 8.6, 8.7, 10.1.6, 10.2, 10.5.6, 10.5.7 and 10.6: Insert related sections according to new template and most are not applicable.
- Section 2.6: Replace original 6.3.3 section to section 2.6 risk and benefit according to new template.
- Section 4.1: Add sentences to emphasize commercial drug shifting has no impact on participation in the study.
- Section 4.2 and 10.7: To remove the license renewal specific date.
- Section 4.3: Clearly identify end of treatment (EOT).
- Section 5.1 and 10.7: The sample size has been increased to approximately 60 patients in total.
- Section 5.3: Update contraceptive text (highly effective methods)
- Section 6.1.1: Update dosing regimen according to new template.
- Section 6.3: Add dose adjustments guidance for QTcF.
- Section 6.3.2.1: Add drug-induced liver injury.
- Section 6.4: Add permitted and prohibited concomitant therapy.

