GI NETs can arise from neuroendocrine cells throughout the gastrointestinal tract. The most frequent sites of origin include the small intestine, stomach, cecum, appendix, colon and rectum (Yao 2008a). Approximately 10% of patients with carcinoid tumors suffer from the classical symptoms of carcinoid syndrome, caused by elevated levels of serotonin ([Barak 2004]). While advanced GI NETs have a reputation for being slowly progressive compared with other tumor types (such as adenocarcinomas), the median survival for patients with metastatic GI NETs varies from 13 months for patients with a gastric primary to 65 months for NETs of small intestinal origin (Yao 2008a).

The bronchopulmonary tree represents another common site of origin of carcinoid tumors, with an annual incidence of approximately 1.4 cases per 100,000 (Yao 2008a). The median survival for patients with lung NETs following metastatic spread is 27 months (Yao 2008a).

Treatment of neuroendocrine tumors

The primary treatment goal for patients with neuroendocrine tumors (NETs) is complete resection of the tumor. If inoperable, the goal is to control tumor growth, to control symptoms if the tumor is functional, and to prolong survival time. Surgical resection represents the traditional first-line therapy of NETs (Plockinger and Wiedenmann 2007). The prognosis following complete surgical resection is generally favorable (Schurr et al 2007). However, curative surgery is often not possible because the majority of patients present with locally advanced, unresectable or metastatic disease. When radical surgery cannot be performed, debulking procedures and resection of metastases (i.e. in liver) may improve the outcome of patients. Guidelines state that surgical resection of liver metastases should be undertaken only if at least 90% of the tumor mass can be removed (Plockinger et al 2004; Eriksson et al 2008). Cytoreductive surgery (tumor debulking) may also render medical therapy more effective by decreasing the secretion of bioactive substances. In patients with jejunio-ileal NETs and liver metastases, the post-surgical 5-year survival rate is approximately 60% compare to 30% in those patients without surgical treatment (Eriksson et al 2008).

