10.8 Sample size calculation

Based on pre-marketing field survey, each year, approximately 6 to 10 patients per site will be newly diagnosed as 'locally advanced, unresectable or metastatic, well differentiated progressive pNET', about 10% to 20% of diagnosed patients will be eligible and agree to participate the study. In order to speed up the enrollment, 5 major sites, where most patients are usually referred to, are selected. Approximately 30 patients were planned in the original protocol based on feasibility. Based on further evaluation after communication with CDE, the sample size was increased to approximately 60 patients to support license renewal. Due to the uncertainties during the enrollment, the actual number of patients may differ from estimations.

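### Inclusion criterion 2 in Protocol 5.2 leaves out metastatic disease, although the study population and the indication include it

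*Protocol*

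**What the plan says.** Criterion 2 in Protocol 5.2 is "Patients must have histological confirmed G1 or G2 locally advanced, unresectable pancreatic neuroendocrine tumors(pNETs) (WHO 2010". The other four criteria cover age, documented progression, measurable disease and the treating physician's recommendation. None concerns metastatic disease.

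Section 5.1, directly above, describes the population as "Chinese adult patients with unresectable, locally advanced or metastatic, G1 or G2 progressive pancreatic neuroendocrine tumors (pNET) (WHO 2010". It also makes the list binding: the investigator "must ensure that only patients who meet all the following inclusion and none of the exclusion criteria are offered treatment in the study".

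The same wider population appears elsewhere in the current protocol:

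- Section 2.1, the indication approved in China: "local advanced, unresectable or metastatic, well differentiated progressive pancreatic neuroendocrine tumors (pNET) without safety and efficacy data in Chinese patients".
- Section 3, the study purpose: "local advanced, unresectable or metastatic, well differentiated progressive pancreatic neuroendocrine tumors".
- Section 10.8, the patients counted in the feasibility survey: "locally advanced, unresectable or metastatic, well differentiated progressive pNET".
- The title, the study design and the population entry in the synopsis, which all include metastatic disease.

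Criterion 2 in the synopsis has no wording on disease extent at all, so the two versions of the same criterion differ. The SAP is also split: Section 3 describes locally advanced disease only, while Section 4 names locally advanced or metastatic disease.

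**The concern.** The text that decides who enters is the text that disagrees with the rest. The study answers a regulator's request for Chinese data in an indication that includes metastatic disease (Protocol 2.1), and Section 2.2 says that the eligibility criteria were designed to follow the Chinese package insert. No section gives a reason for excluding metastatic patients.

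Two outcomes are possible, and sites may differ in which one they produce:

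- **Criterion applied literally.** Patients who qualify only through metastases are screen failures, and that part of the indication goes uncovered.
- **Criterion not applied literally.** Such patients are enrolled but are potential eligibility deviations. Protocol 9.2 requires full verification of adherence to the eligibility criteria, Section 12 permits no authorized deviations, and Section 7.1.6 lists discovered ineligibility as a ground for withdrawal. Violations are tabulated under SAP 5.3.2, and significant ones go into the study report under Protocol 12.

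**Working it through.** **Comparison of the current text.** The plan states no figure on this point, so the first step is to set the wording side by side.

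| Place | Metastatic disease included? |
|---|---|
| Title and study design (synopsis) | yes |
| Synopsis, population | yes |
| Synopsis, criterion 2 | no wording on extent |
| Protocol 2.1, indication | yes |
| Protocol 3 | yes |
| Protocol 5.1 | yes |
| **Protocol 5.2, criterion 2** | **no** |
| Protocol 10.8 | yes |
| SAP 3 | no |
| SAP 4 | yes |

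Amendment 1 lists the sections given one population wording edit: "Section 1.1, 2.1, 3, 5.1, 5.2, 10.8: To add" (the added word is *unresectable*). In the current text five of those six sections include metastatic disease: 1.1, 2.1, 3, 5.1 and 10.8. Only 5.2 does not. Section 1.1 is background on neuroendocrine tumors in general ("the majority of patients present with locally advanced, unresectable or metastatic disease"), so the comparators that define this study are 2.1, 3, 5.1 and 10.8. The log is used here only to show that 5.2 was edited together with the others. The contradiction is between current sections.

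**Who fails.** Criterion 2 asks for disease that is locally advanced and unresectable. A patient with metastases who also has locally advanced, unresectable disease can pass. A patient with metastases who does not have locally advanced disease fails.

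**Size, under stated assumptions.**

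- m, the metastatic share at screening, is not given. Protocol 1.1 says that about 60% of pNET patients have liver metastases; assume m = 0.60.
- f, the fraction of metastatic patients who also have locally advanced, unresectable disease, is not given. It is varied from 0 to 0.75.
- n, the number enrolled after Amendment 1, is about 30 (Protocol 5.1).

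Applied literally, the share of screened patients barred is m × (1 − f). Not applied literally, and with the same m among those enrolled, potential deviations are n × m × (1 − f).

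| f | Share barred, 0.60 × (1 − f) | Potential deviations, 30 × 0.60 × (1 − f) |
|---|---|---|
| 0 | 60% | 18 |
| 0.25 | 45% | 13.5 |
| 0.50 | 30% | 9 |
| 0.75 | 15% | 4.5 |

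With m = 0.60, a majority is barred only if 0.60 × (1 − f) > 0.50, that is, f < 1/6 (16.7%). That threshold moves with m.

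No count is given for the 31 patients enrolled by November 2016, because the version of 5.2 they were screened against is not in the documents.

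**The case against.** The strongest reply is that this is a drafting slip with little practical effect. Section 5.1 states the intended population immediately above the criterion, Section 2.2 ties the criteria to the label, and nothing shows that any site turned a metastatic patient away. A drafting omission is indeed likely. It still sits in the binding text, which sites cannot obtain permission to depart from.

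A second reply concerns the comma. In the title, *unresectable* can be read as an alternative to *locally advanced*. If the comma in 5.2 works the same way, unresectable metastatic disease passes. The cumulative reading is more natural, and Sections 5.1 and 10.8 name metastatic disease separately, which would be redundant if the phrase already covered it. The ambiguity mainly shows that sites could apply the criterion differently.

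A third reply concerns the numbers, and much of it stands. The 60% counts liver metastases among pNET patients generally; it is not the metastatic share among patients with progressive, advanced disease, and f has no source. The table shows a possible scale and is not an estimate.

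Finally, the SAP was finalized in May 2024, so an amendment may come too late to affect screening. That is fair, and it makes disclosure in the study report the likelier remedy.

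**Conclusion.** The contradiction is real and should be corrected. Criterion 2 in 5.2, read literally, bars patients who qualify only through metastatic disease, against the population stated in the title, the synopsis and Sections 2.1, 3, 5.1 and 10.8.

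The share affected is not stated and could be substantial. Assuming 60% metastatic at screening, it runs from 60% down to 15% as the overlap f rises from 0 to 0.75. If the criterion was not applied literally, the corresponding range is 18 down to 4 or 5 potential deviations among about 30 post-amendment patients.

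The analysis is affected only indirectly. The FAS and the Safety Set include every dosed patient, so an enrolled metastatic patient stays in both and the set definitions do not change. Results could still differ if literal screening admits different patients, or if a patient found ineligible is withdrawn and followed for less time. The study is descriptive with a feasibility-based sample size, so no power or error rate is at issue.

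**What to change.** If patients can still be screened, amend the protocol so that criterion 2 in 5.2 and in the synopsis matches the Section 5.1 population, covering unresectable disease that is locally advanced or metastatic, G1 or G2. Use one word order throughout, because the orders in 5.1 and 10.8 can be read differently. Give SAP Sections 3 and 4 the same wording.

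If enrollment is complete, state in the study report how criterion 2 was applied to metastatic patients, how many were enrolled, and how they were classified for deviation reporting. The tumor staging summarized under SAP 5.3.3 supplies the count, and the distribution of affected organs in the same section can support it. The violation tables under SAP 5.3.2 should report these patients; they should not serve to set the criterion aside.

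The cost is short wording changes in two protocol places and two SAP sections. The protocol change needs a written amendment with ethics committee approval and, where required, health authority approval (Protocol 12.1). After enrollment, the cost is one paragraph and one count from data already collected. Sample size, procedures and analysis-set definitions do not change.
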